## **6.6 Withdrawal, Loss to Follow-up, and Study Completion**

### **6.6.1 Voluntary Withdrawal**

Subjects can withdraw from the study at any time; the reason(s) for withdrawal (if given) will be documented. All data available at the time of withdrawal (if any) will be used for analysis, unless the subject has explicitly forbidden the use of such data and has documented this preference in accordance with local regulatory requirements. There will be no further follow-up (per this study protocol) on a subject who has withdrawn. Subjects who withdraw from the study will not be replaced. The withdrawal of a subject can be initiated by the Investigator if he/she determines it is in the best interest of the patient.

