### 6.6.3 Study Completion

A study completion form must be completed for all subjects:

- In whom mortality has been documented
- Who voluntarily withdraw from the study or are withdrawn by the investigator to protect subject rights, welfare, or well-being (§6.6.1)
- Who are lost to follow-up and administratively withdrawn from the study (§6.6.2)
- Who have completed the final protocol-specified follow-up assessment:
  - The final protocol-specified assessment for patients who leave the index procedure catheterization laboratory with an implanted CLAAS device is the 12-month visit (§7.8).

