#### NOTES:

- The definition of AE includes events related to the study device or to the procedures involved but does not imply that there is a relationship between the adverse event and the study device.
- Pre-existing medical conditions or a repeat of symptoms reported prior to the procedure will **not** be reported as an AE. Pre-existing conditions that worsen during a study are to be considered adverse events.
- Planned procedures (scheduled prior to the index procedure) that occur after the index procedure are not considered reportable AEs. Complications from such procedures, however, must be reported.
- Abnormal non-cardiac laboratory findings are not considered a reportable AE unless:
  - The investigator determined that the finding is clinically significant; OR

- o The abnormal laboratory finding required intervention; OR
- o The abnormal laboratory finding required termination of the subject's participation in the study.

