#### **10.3.3 Endpoint Analysis**

All endpoints will be reported in the ITT population using appropriate descriptive statistics. No formal hypothesis testing will be performed. As an additional analysis, all endpoints will be evaluated in the IP population.

All efforts will be made to minimize the amount of missing data; where it occurs, the reasons and counts and percentages of subjects with loss to follow-up will be summarized. In the final analyses, no adjustment will be made for missing data.

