## 14.7 Termination of the Study

The Sponsor reserves the right to terminate the study but intends only to exercise this right for valid scientific or administrative reasons and reasons related to protection of patients. Possible reasons for early trial termination include:

- Unanticipated Adverse Device Effects (UADEs) present an unreasonable risk to patients
- Sponsor decision to suspend or discontinue development of the device

If the trial is terminated early, the Sponsor will provide a written statement to the Investigators to enable notification of the ECs. The Sponsor will also inform the CA (and other regulatory authorities where required). In the case of early termination of trial enrollment, follow-up visits will continue for all enrolled subjects.

The Sponsor may terminate an investigator's or site's participation in the study if there is evidence of an investigator's failure to maintain adequate clinical standards or evidence of an investigator or staff's failure to comply with the protocol. Should investigator or site participation be considered for termination, the Sponsor (or designee) will ensure appropriate follow-up for any subjects enrolled, including transferal to the supervision of an approved investigator and approval of transfer of subject oversight and follow-up by the appropriate EC. Notification of study site suspension or termination will occur no later than five (5) working days after the Sponsor makes the determination. A suspended or terminated study site may not be reinitiated without approval of the reviewing EC. The investigator should notify the EC in writing as soon as possible but no later than within 10 days if the premature termination is related to safety or compliance issues. The same procedure will be applied to other applicable regulatory authorities where required.

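### Section 6.6.1 gives investigator-initiated withdrawal no follow-up rule of its own, so a subject who has not withdrawn consent can drop out of the 6- and 12-month safety and embolic endpoints

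*Combined protocol and SAP*

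**What the plan says.** All references are to Version B of the protocol, which contains the statistical section; section 6.6.1 reads the same in Version A.

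- **Section 6.6.1 (Voluntary Withdrawal), consequence of withdrawal:** "There will be no further follow-up (per this study protocol) on a subject who has withdrawn". Data already collected are kept, unless the subject has forbidden their use: "All data available at the time of withdrawal (if any) will be used for analysis". Also, "Subjects who withdraw from the study will not be replaced".
- **Section 6.6.1, last sentence of the same paragraph:** "The withdrawal of a subject can be initiated by the Investigator if he/she determines it is in the best interest of the patient". No separate consequence is attached to this route.
- **Section 6.6.3 (Study Completion):** a completion form is required for subjects "Who voluntarily withdraw from the study or are withdrawn by the investigator to protect subject rights, welfare, or well-being". Both routes share one bullet, which points back to 6.6.1.
- **Section 8.8.1:** adverse events are collected from enrollment until the study closes. Withdrawn subjects are not mentioned.
- **Sections 5.3.3 to 5.3.3.3:** mortality, major safety events and embolic events are evaluated in hospital, at 45 days, and at 6 and 12 months.
- **Section 10.3.3:** "In the final analyses, no adjustment will be made for missing data".

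**The concern.** Withdrawal of consent obliges the study to stop. An investigator's judgement that study participation no longer suits a subject does not in itself oblige the study to stop asking whether that subject is alive or has had a stroke. Section 6.6.1 does not separate the two.

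The treatment is a one-time permanent implant. For a subject who still carries the device, leaving the study ends observation and not exposure. The stated grounds for investigator withdrawal are the patient's interest (6.6.1) and the subject's rights, welfare or well-being (6.6.3). Withdrawals on such grounds may well be related to prognosis, though the documents do not say so. If they are, the subjects lost are more likely than average to have a later event, and the observed 6- and 12-month rates would be too low. In an open-label, single-arm, single-center study there is no comparator in which the same loss would show. Section 4.3 says the results are to inform the design of a pivotal trial.

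**Working it through.** There is no planned figure to reproduce. Section 10.1 gives 20 subjects without a rate, precision target or power, and no hypothesis is tested. The check is a reading of the text, followed by an illustration of size.

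**Step 1. Does the no-follow-up rule reach investigator withdrawals?** The rule and the investigator's power to withdraw stand in the same paragraph. Section 6.6.3 lists investigator withdrawals as study exits and cites 6.6.1 for them. No other section says what follow-up they receive. The natural reading is that the rule applies.

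**Step 2. Does other text restore the follow-up?** Section 8.8.1 could be read that way, since adverse event collection runs to study closure. It makes no exception to 6.6.1, and 6.6.1 makes none for it. A site cannot tell which governs, so the two sections are in tension.

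**Step 3. Which endpoints are exposed?** Only assessments after the withdrawal date.

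| Endpoint | Time point | Exposed to |
|---|---|---|
| Primary safety | Later of discharge and day 7 | Withdrawal before then |
| Primary performance (closure) | 45 days | Withdrawal before then |
| Mortality, major safety events, embolic events | To 6 and 12 months | Any withdrawal before those visits |

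Events before withdrawal stay in the numerator. A subject withdrawn after a stroke already counts in major safety events (overt CNS injury) and, if the stroke was ischemic, in embolic events. A later death then changes mortality only.

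**Step 4. Size.** Inputs: N = 20 (section 10.1). The number withdrawn, w, is assumed to be 1 to 3, because no rate is given. The number of observed events is x. Each withdrawn subject is assumed to have had no earlier event for the endpoint in question. Available-case denominators are also assumed, because section 10.3.3 does not state the denominator.

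- Available-case rate = x/(N − w)
- Best case = x/N
- Worst case = (x + w)/N

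With x = 0 (exact Clopper-Pearson 95% intervals in brackets, added here; the plan specifies only counts and percentages):

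| w | Available case | Worst case |
|---|---|---|
| 0 | 0/20 = 0% (0 to 16.8%) | 0/20 = 0% (0 to 16.8%) |
| 1 | 0/19 = 0% (0 to 17.6%) | 1/20 = 5% (0.1 to 24.9%) |
| 2 | 0/18 = 0% (0 to 18.5%) | 2/20 = 10% (1.2 to 31.7%) |
| 3 | 0/17 = 0% (0 to 19.5%) | 3/20 = 15% (3.2 to 37.9%) |

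Each withdrawn subject widens the best-to-worst range by 1/20 = 5 percentage points. With x = 1 and w = 2, the available-case rate is 1/18 = 5.6%, against a range of 1/20 = 5% to 3/20 = 15%. When no event is observed, keeping all 20 in the denominator does not help: 0/20 is also 0%.

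**The case against.** **The rule may not cover investigator withdrawals.** The section title refers to voluntary withdrawal, the no-follow-up sentence speaks of a subject who has withdrawn, and the investigator sentence comes after it. Section 6.6.2 exempts only those who left voluntarily from its tracing efforts. This narrower reading is possible, and it shows that the text is ambiguous. It does not remove the problem: 6.6.3 ties investigator withdrawals to 6.6.1, and no section gives them any other follow-up.

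**The effect is limited.** This stands. The study is small and descriptive, the primary endpoints fall early, data up to withdrawal are kept, and the rule bars only follow-up under this protocol, not routine care. The completion form and the endpoint listings should make one or two withdrawals visible. They would not show what happened afterwards.

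**Four stronger readings are tempting and not supported.**

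- A reader might infer that the protocol expects adverse findings to lead to withdrawal, because the section 8.1 notes contain "The abnormal laboratory finding required termination of the subject's participation in the" study. That item is only one of three conditions that make an abnormal non-cardiac laboratory result reportable. It does not predict or instruct withdrawal after clinical events.
- A reader might infer that subjects are withdrawn after a stroke and their events lost. The event would already be counted, and sections 7.5 and 7.7 to 7.9 require repeat assessment 90 ± 14 days after a confirmed stroke, which points towards keeping such subjects.
- A reader might apply the permanent-exposure argument to everyone withdrawn. It does not hold for a subject whose device has been removed.
- A reader might take section 14.7 as a contrary rule for the same situation: "In the case of early termination of trial enrollment, follow-up visits will continue for all enrolled subjects". That concerns a sponsor decision to stop enrollment, where no subject has been withdrawn, so the comparison is loose.

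**Conclusion.** The point holds in a limited form. Section 6.6.1, read with 6.6.3, permits follow-up under the protocol to end for a subject who has not withdrawn consent and still has the implant, and it is unreconciled with 8.8.1. With no adjustment for missing data, later deaths, or first later safety or embolic events, can be missed at 6 and 12 months.

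In the illustration, one such event turns 1/20 (5%) into 0/19 (0%), and two turn 2/20 (10%) into 0/18 (0%). This rests on assumed withdrawal and event counts, available-case denominators, and mortality or subjects with no earlier event for that endpoint. That such subjects are sicker than average is an inference from the stated grounds for withdrawal, and that they still consent is an inference from the absence of any consent condition. The documents establish neither. The direction of bias is therefore plausible but not shown. The primary endpoints are affected only by withdrawal before their own time points. This is a worthwhile and cheap improvement; it does not invalidate the design.

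**What to change.** Amend 6.6.1 to separate two cases.

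- **(a) The subject withdraws consent:** follow-up stops, as now written.
- **(b) The investigator decides on withdrawal and consent stands:** the subject stays in the study for collection of vital status, QVSFS, adverse events and documentation of concomitant medication at the remaining scheduled time points, unless consent is later withdrawn. Telephone contact is acceptable; telephone QVSFS is already in use at day 7.

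In 6.6.3, have the completion form for (b) filled in at month 12 or at death. Report (a) and (b) separately in the disposition summary. Reconcile 6.6.1 with 8.8.1 so that the period of adverse event collection is clear for each case.

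This change concerns data collection only and takes no position on which imaging or treatment should stop or continue. It would therefore not by itself recover 6- or 12-month closure data. For the clinical endpoints, if the contacts succeed, the denominator stays at 20 and the 5-point gap per subject in case (b) falls to zero.

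The cost is a short amendment, a sentence in the consent form saying that safety contacts may continue after an investigator decision, and a few telephone calls per affected subject. The subject's right to leave is unchanged.

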### **6.6.2 Loss to Follow-up**

When a subject does not return for a clinic visit or is not reachable for a telephone contact, this event is considered a missed visit. Subjects with a missed visit may return for subsequent follow-up visits.

If a subject has a missed visit and has not voluntarily withdrawn from the trial, site personnel should make all reasonable efforts to locate and communicate with the subject, including the following, at each contact time point:

- A minimum of (3) three telephone calls to contact the subject should be recorded in the source documentation, including date, time, and initials of site personnel trying to make contact.
- If these attempts are unsuccessful, a letter should be sent to the subject.

Subjects with three consecutive missed visits, despite the above-mentioned communication attempts, will be considered lost to follow-up and administratively withdrawn from the study.

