## 5.0 Study Design

### 5.1 Study Design Overview

This prospective, single center, open-label, single arm, study will enroll up to 20 subjects aimed at examining the safety and technical performance of the CLAAS device for LAA closure. Patients with non-valvular atrial fibrillation who are at increased risk for stroke and systemic embolism based on CHA2DS2-VASc scores, and who are recommended for oral anticoagulation therapy but have an appropriate rationale to seek a non-pharmacologic alternative to oral anticoagulation, and who meet all eligibility criteria, will be enrolled in the study and undergo LAA closure with the CLAAS system.

Subjects will have clinical follow-up prior to hospital discharge and at 7 days, 45 days, and 6- and 12-months post procedure. Transesophageal echocardiographic (TEE) follow-up will be performed at 45 days and, 6 and 12 months in all subjects.

The primary safety endpoint is freedom from major adverse events, evaluated at hospital discharge or at 7 days post-procedure (whichever occurs later), and defined as absence of the composite of all-cause mortality, ischemic stroke, systemic thromboembolism, and device- or procedure-related adverse events requiring open cardiac surgery or major endovascular intervention. The primary performance endpoint is closure success, defined as device success followed by successful LAA closure (complete closure or peri-device residual leak ≤5 mm in width on TEE at 45 days post-procedure). The study will also report additional secondary safety, performance, and effectiveness endpoints, as well as using TEE to confirm post-procedure ICE evaluation of device seal and position as a comparator for device success.

All endpoints will be reported using appropriate descriptive statistics in the primary analysis population (the ITT population), and no hypothesis testing will be performed. As a secondary analysis, all endpoints will be evaluated in the Implanted Patient (IP) population.

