## 7.8 Six-month Follow-up (Clinic Visit)

All subjects who received a CLAAS implant will return to the clinic at 6 months ( $\pm$  30 days) to include the following assessments:

- Physical examination
- Stroke assessment, to include:
  - Questionnaire for Verifying Stroke Free Status (QVSFS)
  - NIH Stroke Scale (NIHSS); the NIHSS must be performed by a neurologist or NIHSS-certified research staff
  - Patients in whom a neurologic event is suspected on the basis of the QVSFS, NIHSS, or other signs or symptoms will require a neurologic examination and evaluation performed by a neurologist or clinical designee (e.g., neurology fellow). In patients with confirmed stroke, NIHSS and mRS must be documented, and repeated  $90 \pm 14$  days post-event.
- A transesophageal echocardiogram (TEE).
- Current concomitant medications documentation. If DAPT has been interrupted or terminated the stop date (and resumption date, if applicable) and the reason for interruption/termination should be recorded. If monotherapy has been initiated due to high bleeding risk, the factors contributing to the high bleeding risk assessment should be documented.
- Documentation of any adverse events occurring since the previous evaluation.

Prior to concluding the visit, research staff should also review the follow-up requirements with the subject to help ensure that the patient returns to the clinic for the 12-month follow-up visit

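### The three-consecutive-missed-visits rule cannot classify anyone seen at day 45 as lost to follow-up, so late dropouts would be misclassified in the planned summary

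*Combined protocol and SAP*

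**What the plan says.** The references are to protocol Version B; Version A has the same rule and the same follow-up visits.

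- **Missed visit (6.6.2).** When a subject "does not return for a clinic visit or is not reachable for a telephone contact, this event is considered a missed visit". The day-7 telephone call therefore counts as a visit.
- **Lost to follow-up (6.6.2).** "Subjects with three consecutive missed visits, despite the above-mentioned communication attempts, will be considered lost to follow-up and administratively withdrawn from the study". The protocol has no other definition.
- **Schedule (5.1 and Table 3 in 7.1).** "Subjects will have clinical follow-up prior to hospital discharge and at 7 days, 45 days, and 6- and 12-months post procedure".
- **Who attends what (7.6 to 7.9).** The 7-day and 45-day contacts are for all subjects. The later visits are narrower: "All subjects who received a CLAAS implant will return to the clinic at 6 months", and 7.9 limits the 12-month visit in the same way.
- **End of follow-up (6.6.3).** "The final protocol-specified assessment for patients who leave the index procedure catheterization laboratory with an implanted CLAAS device is the 12-month visit". No final assessment is named for subjects enrolled but not implanted.
- **Completion form (6.6.3).** It is triggered by death, by withdrawal (the subject's or the investigator's), by completing the final assessment, or for subjects "Who are lost to follow-up and administratively withdrawn from the study".
- **Missing data (10.3.3).** Where data are missing, "the reasons and counts and percentages of subjects with loss to follow-up will be summarized". The section adds: "In the final analyses, no adjustment will be made for missing data".

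**The concern.** The threshold is long relative to the schedule. Few contacts follow day 45, so the rule may be unable to identify the subjects it is meant to count: those who complete the early visits and then drop out of contact.

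What is at stake is the disposition account behind the 6- and 12-month secondary endpoints: mortality, major safety events, embolic events and later closure success. Section 10.3.3 makes no adjustment for missing data, so a reader depends on that account to judge how far the late results can be trusted. Section 4.3 says the study is to inform a pivotal trial, and the attrition rate is a direct input to planning one.

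**Working it through.** The plan states no dropout rate or expected loss, so there is no figure to reproduce. The check lists every attended/missed pattern and looks for a run of three misses.

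**Inputs**
- Run needed: k = 3 (6.6.2); an unanswered telephone contact counts as a miss (6.6.2).
- Implanted subjects, contacts after discharge: 7 d, 45 d, 6 m, 12 m, so n = 4 (5.1, Table 3, 7.6 to 7.9).
- Non-implanted subjects, contacts after discharge: 7 d, 45 d, so n = 2 (7.6 to 7.9).
- Target enrolment: 20 (10.1).

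**Step 1. Possible runs, implanted.** The number of runs is n − k + 1 = 4 − 3 + 1 = 2. They are {7 d, 45 d, 6 m} and {45 d, 6 m, 12 m}. Both contain day 45.

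**Step 2. Patterns, implanted.** There are 2^4 = 16.
- Three meet the rule: only 12 m attended; only 7 d attended; none attended.
- Day 45 attended: 2^3 = 8 patterns, of which 0 meet the rule.
- 12 m missed: 2^3 = 8 patterns, of which 2 meet the rule. The other 6 are 4 with day 45 attended and 2 with day 45 missed but 6 m attended.

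**Step 3. Count the pre-discharge assessment as a visit.** Now n = 5, giving 3 runs; the added run is {pre-discharge, 7 d, 45 d}, which also contains day 45. Of 2^5 = 32 patterns 8 meet the rule; of the 16 with day 45 attended, 0 do.

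**Step 4. Non-implanted.** n = 2 is less than k = 3, so no run exists and 0 of 2^2 = 4 patterns meet the rule. Counting pre-discharge gives one run, met by 1 of 2^3 = 8 patterns, and it requires missing an in-hospital assessment.

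**Step 5. Sensitivity to a longer schedule.** Section 8.8.1 mentions a 5-year telephone contact, and the QVSFS form in Appendix C has boxes for years 2 to 5. If yearly contacts in years 2 to 5 existed, n = 8. Of the 2^7 = 128 patterns with day 45 attended, 40 would meet the rule, the earliest run being {6 m, 12 m, 2 y}.

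**Step 6. Size.** Each late dropout is 1/20 = 5 percentage points. As an assumption, since the documents give no rate: if 2 to 4 of 20 become unreachable after day 45, true loss is 2/20 = 10% to 4/20 = 20%, while the rule counts 0.

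The pattern counts show what the rule can and cannot detect. They are not probabilities.

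**The case against.** The strongest reply is that little is concealed. Section 10.3.1 reports binary endpoints with their sample size, so the 6- and 12-month denominators will show the shortfall. Section 6.7 treats an assessment not done, or done outside its window, as a collected deviation. Section 10.3.4 tabulates deviations by type and lists primary and secondary endpoints, and in about 20 subjects such listings reveal each gap. Late deaths and withdrawals have their own documentation. The sentence in 10.3.3 can also be read as promising reasons for missing data generally; it does not cite 6.6.2, and 10.3.1 defers further detail to a formal SAP.

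All of this stands. A reader might infer that the report would hide substantial late missingness behind a 0% figure, and the documents do not support that. What remains is that denominators and deviation counts do not by themselves give a subject's final status or separate an unreachable subject from one who skipped an assessment.

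The second reply is that the word 'never' depends on follow-up ending at 12 months, which 8.8.1 and the QVSFS form contradict. That limits the finding to the 12-month schedule. The synopsis, Table 3 and 6.6.3 all end there, so it is the better-supported reading, but the conflict needs resolving.

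A reader might also see harm in the opposite case: a subject who misses 7 days, 45 days and 6 months is withdrawn before the 12-month visit. This would matter only for someone unreachable at three contacts, despite at least three calls and a letter each time, who would then have attended. It is a side issue of little consequence.

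**Conclusion.** The point holds as a misclassification. Under the 12-month schedule, no subject who attends day 45 can meet the 6.6.2 rule (0 of 8 patterns, or 0 of 16 with pre-discharge counted). Nor can any non-implanted subject meet it on post-discharge contacts (0 of 4). If 10.3.3 uses the 6.6.2 definition, its count for dropouts after day 45 is zero whatever happens. Unless they die or are withdrawn, these subjects also fall outside every completion-form trigger in 6.6.3.

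The conclusion rests on two assumptions: that follow-up ends at 12 months, and that the summary uses the protocol's only definition of loss. The size is 5 percentage points per affected subject at the target of 20; the 10 to 20% range is illustrative only.

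The primary endpoints (discharge or 7 days, and day 45) are unaffected for these subjects. The 6- and 12-month secondary endpoints are the ones concerned, and there the estimates do not change; the account of who is missing and why does. The correction is worth making because a stated rule gives a wrong count and is cheap to repair.

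**What to change.** 1. **6.6.2.** Define a subject as lost to follow-up if the subject did not attend his or her own final scheduled visit (12 months if implanted; the last required visit if not), was not reached despite the calls and letter already specified, and has not died or been withdrawn by choice or by the investigator. Date the loss at last contact. If administrative withdrawal after three misses is kept, state that those subjects count as lost. Tying the definition to the subject's own final visit matters: a blanket 12-month criterion would wrongly capture non-implanted subjects who completed everything required of them.
2. **6.6.3.** Require a completion form for every enrolled subject, and name the final assessment for non-implanted subjects.
3. **10.3.3.** For each endpoint and visit, report the number expected, the number evaluable and the number missing by reason (death, withdrawal, lost, missed visit, imaging not done).
4. **8.8.1 and Appendix C.** Reconcile the 5-year contact and the year 2 to 5 boxes with the 12-month end of study.

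The cost is a few sentences and one disposition table, with no new assessments. The downside is that the reported loss figure may look less favourable.
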